### C.3.4 Investigational Centers

Site distribution is anticipated to include up to 75 centers in the United States, 10 in Canada and 30 in Europe.

For this study, the following investigator/center selection minimum criteria are considered:

- Center must have sufficient patient population
- Each center's Implant Team (i.e. 1st and 2nd operators) must have completed at least 30 cumulative TAVI procedures
- There will be no other study ongoing during this study duration, which would prevent the center from meeting enrollment goals for SURTAVI or provide adequate staffing
- Investigator should have adequate staff that is accessible and has time to manage the study for 7 days per week, 24 hours per day
- Investigator, co-investigators, and study staff must be willing to provide his/her Curriculum Vitae
- Investigator and co-investigators must be willing to sign and comply with the protocol-specific Investigator Agreement
- Center must be willing to comply with the Clinical Investigation Plan and data requirements, including reporting Adverse Events
- Center has demonstrated experience with conducting clinical (device) trials that comply with applicable regulatory standards
- Center is willing to participate in follow-up of patients for 5 years
- Center has an internet connection with sufficient speed of data transfer

All investigators will be appropriately qualified practitioners legally entitled to practice, and experienced in the diagnosis and treatment of patients requiring an aortic valve treatment with a TAVI or SAVR.

For the purposes of the SURTAVI trial, it is imperative that Medtronic leverages highly qualified surgeons for the surgical aortic valve replacements (SAVR) that will occur as a part of the trial. The following minimum criteria will be used for all cardiac surgeons performing SAVRs in the SURTAVI trial:

- At least 5 years of experience post-residency
- At least 100 career aortic valve replacements post-residency
- At least 75 valve procedures in the last 3 years
- At least 35 surgical aortic valve replacements in the last 3 years
- At least 15 aortic valve replacements in the last year

### C.3.5 *Number of Subjects*

Up to 2000 subjects will be randomized [1:1, TAVI: Surgical Aortic Valve Replacement (SAVR)]. The enrollment phase is anticipated to be approximately 36 months. Subjects will be followed through 5 years for assessment of long-term safety and efficacy endpoints. The total trial duration is expected to be approximately 8 years.

Enrollments shall not exceed 20% (approximately 400) of total randomized subjects at any individual site. Enrollment is competitive; therefore there is no set minimum number of subjects to be enrolled per site. Appropriate measures will be taken to monitor enrollment across geographies to ensure at least 40% of the total patient population is enrolled within the United States.

### C.3.6 *Inclusion/Exclusion Criteria*

#### C.3.6.1 Inclusion Criteria

To participate in this trial, the subject must meet ALL of the following inclusion criteria.

1. Subject must have co-morbidities such that Heart Team agrees predicted risk of operative mortality is  $\geq 3\%$  and  $< 15\%$  at 30 days (Intermediate Clinical Risk classification). Heart team evaluation of clinical surgical mortality risk for each patient includes the calculated STS score for predicted risk of surgical mortality augmented by consideration of the overall clinical status and co-morbidities unmeasured by the STS risk calculation;
2. Heart Team unanimously agree on treatment proposal and eligibility for randomization based on their clinical judgment (including anatomy assessment, risk factors, etc.);
3. Subject has severe aortic stenosis presenting with:
  - a) Critical aortic valve area defined as an initial aortic valve area of  $\leq 1.0 \text{ cm}^2$  or aortic valve area index  $< 0.6 \text{ cm}^2/\text{m}^2$

**AND**

  - b) Mean gradient  $> 40\text{mmHg}$  or  $V_{\text{max}} > 4\text{m/sec}$  by resting echocardiogram or simultaneous pressure recordings at cardiac catheterization [or with dobutamine stress, if subject has a left ventricular ejection fraction (LVEF)  $< 55\%$ ] or velocity ratio  $< 0.25$ ;
4. Subject is symptomatic from his/her aortic valve stenosis, as demonstrated by New York Heart Association (NYHA) Functional Class II or greater;
5. Subject and the treating physician agree that the subject will return for all required post-procedure follow-up visits;
6. Subject meets the legal minimum age to provide informed consent based on local regulatory requirements.

#### C.3.6.2 Exclusion Criteria

Subjects are NOT eligible for trial participation if they meet ANY of the following exclusion criteria:

1. Subject has refused surgical aortic valve replacement (SAVR) as a treatment option;
2. Any condition considered a contraindication for placement of a bioprosthetic valve (i.e. subject requires a mechanical valve);

3. A known hypersensitivity or contraindication to all anticoagulation/antiplatelet regimens (or inability to be anticoagulated for the index procedure), nitinol, or sensitivity to contrast media which cannot be adequately pre-medicated;
4. Blood dyscrasias as defined: leukopenia (WBC <1000mm^3), thrombocytopenia (platelet count <50,000 cells/mm^3), history of bleeding diathesis or coagulopathy;
5. Ongoing sepsis, including active endocarditis;
6. Any condition considered a contraindication to extracorporeal assistance;
7. Any percutaneous coronary or peripheral interventional procedure performed within 30 days prior to randomization (Subjects with recent placement of drug eluting stent(s) should be assessed for ability to safely proceed with SAVR within the protocol timeframe);
8. Symptomatic carotid or vertebral artery disease or successful treatment of carotid stenosis within six weeks of randomization;
9. Cardiogenic shock manifested by low cardiac output, vasopressor dependence, or mechanical hemodynamic support;
10. Recent (within 6 months of randomization) cerebrovascular accident (CVA) or transient ischemic attack (TIA);
11. Active gastrointestinal (GI) bleeding that would preclude anticoagulation;
12. Subject refuses a blood transfusion;
13. Severe dementia (resulting in either inability to provide informed consent for the trial/procedure, prevents independent lifestyle outside of a chronic care facility, or will fundamentally complicate rehabilitation from the procedure or compliance with follow-up visits);
14. Multivessel coronary artery disease with a Syntax score >22 and/or unprotected left main coronary artery (Syntax score calculation is not required for patients with history of previous revascularization if repeat revascularization is not planned);
15. Estimated life expectancy of less than 24 months due to associated non-cardiac co-morbid conditions;
16. Other medical, social, or psychological conditions that in the opinion of the Investigator precludes the subject from appropriate consent or adherence to the protocol required follow-up exams;
17. Currently participating in an investigational drug or another device trial (excluding registries);
18. Evidence of an acute myocardial infarction ≤30 days before the index procedure;
19. Need for emergency surgery for any reason;
20. True porcelain aorta (i.e. Heart Team agrees the aorta is not clampable for SAVR);
21. Extensive mediastinal radiation;
22. Liver failure (Child-C);
23. Reduced ventricular function with left ventricular ejection fraction (LVEF) <20% as measured by resting echocardiogram;
24. Uncontrolled atrial fibrillation (eg. resting heart rate >120bpm);
25. Pregnancy or intent to become pregnant prior to completion of all protocol follow-up requirements;
26. End stage renal disease requiring chronic dialysis or creatinine clearance < 20 cc/min;
27. Pulmonary Hypertension (systolic pressure> 80mmHg);
28. Severe Chronic Obstructive Pulmonary Disease (COPD) demonstrated by Forced Expiratory Volume (FEV1) < 750cc;
29. Frailty assessments identify:
  - Subject is < 80 years of age and three or more of the following apply
  - Subject is ≥ 80 years of age and two or more of the following apply
    - Wheelchair bound
    - Resides in an institutional care facility (eg. nursing home, skilled care center)
    - Body Mass Index < 20 kg/m^2
    - Grip strength <16 kg
    - Katz Index score ≤ 4

- o Albumin < 3.5 g/dL;
- 30. Marfan syndrome or other known connective tissue disease that would necessitate aortic root replacement/intervention.

**Anatomical Exclusion Criteria**

- 31. Native aortic annulus size <18 mm or >29 mm per the baseline diagnostic imaging;
- 32. Pre-existing prosthetic heart valve in any position;
- 33. Mixed aortic valve disease [aortic stenosis and aortic regurgitation with predominant aortic regurgitation (3-4+)];
- 34. Severe mitral or severe tricuspid regurgitation;
- 35. Severe mitral stenosis;
- 36. Hypertrophic obstructive cardiomyopathy;
- 37. Echocardiographic or Multislice Computed Tomography (MSCT) evidence of new or untreated intracardiac mass, thrombus or vegetation;
- 38. Ascending aorta diameter greater than maximum diameter relative to the native aortic annulus size:

Aortic Annulus Diameter	Ascending Aorta Diameter
18 mm – 20 mm	>34 mm
20 mm – 23 mm	>40 mm
23 mm – 29 mm	>43 mm

- 39. Aortic root angulation (angle between plane of aortic valve annulus and horizontal plane/vertebrae):
  - a) Femoral and left subclavian/axillary access > 70°

**OR**

  - b) Right subclavian/axillary access: Aortic root angulation > 30°;
- 40. Congenital bicuspid or unicuspid valve verified by echocardiography;
- 41. Sinus of Valsalva anatomy that would prevent adequate coronary perfusion.

**Vascular Exclusion Criteria**

- 42. Transarterial access not able to accommodate an 18Fr sheath.

### C.3.7 *Informed Consent*

The investigator must obtain written informed consent prior to subjecting the subject to any trial related activity.

Well in advance of the consent discussion, the subject should receive the MEC/IRB approved Patient Information and Informed Consent Form (ICF). During the consent discussion the investigator or his/her designee must fully inform the subject of all pertinent aspects of the trial including the approval of the MEC/IRB of the written Patient Information. If a subject is illiterate, an impartial witness must be present during the entire informed consent discussion. All items discussed in the Patient Information and the ICF must be explained. The language used shall be in the subject's native language, as non-technical as possible and must be understandable to the subject and the impartial witness, where applicable.

The subject must have ample time and opportunity to inquire about details of the trial, and to decide whether or not to participate in the clinical trial. All questions about the trial should be answered to the satisfaction of the subject.

Neither the investigator, nor the investigation site staff shall coerce or unduly influence a subject to participate or to continue to participate in the clinical trial. The informed consent process shall not appear to waive the subject's rights.

When the subject decides to participate in the clinical trial, the ICF must be signed and personally dated by the subject and investigator. If applicable, the witness shall also sign and personally date the consent form to attest that the information in the Patient Information and Informed Consent Form was accurately explained and clearly understood by the subject, and that informed consent was freely given.

Signing the ICF serves to document the written and verbal information that the Investigator or authorized delegate provides to the patient, the patient understanding of the information, and their agreement to participate. The Investigator or authorized delegate must document in the patient's medical records that the patient was consented and the date on which the consent was obtained. The original signed consent form will be retained in the patient's trial records. A copy of the informed consent will be provided to the patient and a copy placed in the patient's medical record.

Data relating to the trial might be made available to third parties (for example in case of an audit performed by regulatory authorities), provided the data are treated as confidential and that the subject's privacy is guaranteed. In the United States, "Protected Health Information" will be maintained in compliance with the Health Insurance Portability and Accountability Act of 1996 (HIPAA).

[figure not shown]
### C.3.8 *Revisions in Patient Information and Informed Consent Form*

Medtronic will inform the investigators whenever information becomes available that may be relevant to the subject's continued participation in the trial. The revised information will be sent to the investigator for approval by the IRB/MEC. After approval by the IRB/MEC, a copy of this information must be provided to the participating subjects, and the informed consent process as described above needs to be repeated. The investigator or his/her designee should inform the subject in a timely manner.

C.3.9 Enrollment Flowchart for Randomization to TAVI or SAVR

Figure 1: Enrollment Flowchart

If the patient meets all of the inclusion criteria and none of the exclusion and Heart Team determines the patient is eligible for randomization in the SURTAVI trial, subjects will be randomized on a 1:1 basis to either TAVI or SAVR. Randomization will be stratified by the need for coronary revascularization. In case of required coronary revascularization, concomitant percutaneous coronary intervention (PCI) and TAVI is encouraged; however staging is left at the discretion of the operator. Coronary artery bypass graft (CABG) should be conducted during the index procedure.

C.3.10 Trial Training

Prior to investigational site activation or subsequent involvement in trial activities, Medtronic (or designee) will provide trial training relevant and pertinent to the involvement of personnel conducting trial activities, including investigator responsibilities, adverse event reporting as well as device training (if necessary, usage and handling of device under investigation). Training may be conducted via Site Initiation Visits, Investigator and Coordinator Meetings, and/or other media sessions. The sponsor will maintain documentation of attendance at each of these training opportunities, as applicable.

Additionally, Medtronic representative(s) may be present at each site's TAVI procedures as part of the ongoing training process.

## C.4 Trial Procedures

### C.4.1 Screening Procedures

Prior to any trial-specific tests or procedures, written informed consent must be obtained from the subject. Failure to obtain a signed and hand dated informed consent prior to the procedure constitutes a protocol violation, which is reportable to the IRB/MEC, the Food and Drug Administration (FDA), and other regulatory authorities as applicable.

All potential subjects for trial entry must be screened for eligibility. All patients with symptomatic severe AS that provide informed consent will be entered into the Electronic Data Capture (EDC) system and total number of patients screened will be counted. The reasons why a patient did not enter the Heart Team meeting will be collected (eg. patient does not meet inclusion criteria or meets an exclusion criteria) and, age, STS score, and available screening data.

Data readily available in the patient's medical record may be utilized to fulfill screening requirements and do not need to be repeated. If not previously completed, the following tests and procedures must be performed prior to randomization to verify eligibility. The recommended timeframe for these tests and procedures is within 30 days prior to submission to the Heart Team, unless otherwise specified.

- Demographics and Medical History
- Clinical Assessments – Refer to **Appendix R.19**
  - 5-Meter Gait Speed
  - Grip Strength
- Physical Examination including:
  - Vital signs, weight, height, and body surface area (BSA);
    - BSA will be calculated from height and weight by use of the formula by Dubois and Dubois ( $BSA = 0.007184 \times \text{weight [kg]}^{0.425} \times \text{height [m]}^{0.725}$ )
  - Major systems findings
- NYHA Classification
- Risk Assessments:
  - STS Risk Score – Dataset Version 2.73
  - Logistic EuroSCORE
  - EuroSCORE II
  - SYNTAX Score
  - Katz Index of Independence in Activities of Daily Living
- Co-morbidities
- Routine Laboratory Tests:
  - Complete Blood Count:
    - White Blood Count
    - Hematocrit
    - Hemoglobin
    - Platelet Count
  - Creatinine and Creatinine Clearance
  - Cardiac Enzymes (CK/CK-MB)
  - International Normalized Ratio (INR), if applicable
  - Activated Partial Thromboplastin Time (aPTT)
  - B-type Natriuretic Peptide (BNP) or NT-proBNP
  - Liver Panel:
    - ALT
    - AST
    - Albumin
  - Sodium
  - Potassium

- Transthoracic Echocardiogram (TTE)
  - Comprehensive transthoracic two-dimensional (2D) echocardiogram (TTE) is required within 365 days prior to review by the Heart Team to confirm diagnosis of severe aortic stenosis(AS) including:
    - Aortic valve area / indexed aortic valve area
    - Mean gradient / peak velocity / velocity ratio
  - If a historical TTE is used to confirm AS diagnosis a repeat TTE must be performed within 45 days prior to review by the Heart Team to:
    - Assess:
      - Aortic regurgitation
      - Mitral and tricuspid valve status (stenosis and regurgitation)
      - LVEF
    - Rule out:
      - New or recent MI
      - New or untreated intracardiac mass, thrombus or vegetation
      - Congenital bicuspid or unicuspid valve
  - If the patient recently underwent balloon aortic valvuloplasty (BAV), a TTE should be obtained post-BAV; within 45 days prior to review by the Heart Team to reconfirm all inclusion/exclusion echocardiographic parameters
  - Protocol required echocardiograms should be performed according to the Echocardiography Procedures found in **Appendix R.7**.
- Multi-Slice Computed Tomography (MSCT) Angiogram
  - Multi-Slice Computed Tomography (MSCT) angiograms with complete visualization of both iliacs, femorals and aorta (and subclavian/axillaries, if applicable), up to and including the aortic annulus. In the situation where subjects have compromised renal function that precludes contrast media, Magnetic Resonance (MR) imaging may be used as an alternative. MSCT angiograms should be performed according to the Computed Topography (CT) Angiography Acquisition Guidelines found in **Appendix R.9**. If the MSCT angiogram was conducted in the last 365 days and subject has not had a peripheral vascular intervention since the time of the image, a more recent exam is not required as long as visualization of both iliacs and femorals (and subclavian/axillaries, if applicable) to the aorta can be viewed. However, if the subject had a peripheral vascular intervention, the exam must be repeated after the intervention and within 90 days of review by the Heart Team.
- Coronary Arteriogram
  - Selective coronary arteriography to assess the presence and severity of coronary artery disease which should include angiograms of both coronary arteries and all bypass grafts (if applicable). If the coronary arteriogram has been performed within the last 365 days and the subject qualifies for the trial (no significant coronary artery disease), a more recent exam is not required. However, if the subject had evidence of significant coronary artery disease and/or received a coronary intervention, the exam must be repeated after the intervention and within 90 days of review by the Heart Team.
- 12-lead Electrocardiogram (ECG)

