### **18. Echo Core Lab Analysis**

Data generated by the Echo Core Lab will be the primary data used for analysis and reporting. Qualitative assessment of valvular regurgitation will be performed using the criteria previously described in sections 8 and 9 of this Appendix. The Echo Core Lab will report the following variables:

- Aortic annulus long-axis diameter in mid-systole (screening/baseline only)
- LVOT long axis diameter in mid-systole
- Sinus of Valsalva diameter (SOV) at end diastole (screening/baseline only)
- Sino-tubular junction diameter (STJ) at end diastole (screening/baseline only)
- Sinus of Valsalva height (SOVH) at end-diastole (screening/baseline only)
- Device location and migration
- Max aortic valve velocity (V2) by CW Doppler
- Velocity time integral (VTI) across aortic valve by CW Doppler
- Mean gradient across aortic valve (MGV2) by CW Doppler
- Peak LVOT velocity (V1) by PW Doppler
- Velocity Ratio (V1 / V2)
- Velocity time integral (VTI) of LVOT velocity by PW Doppler
- Mean LVOT gradient (MGV1) by PW Doppler
- Doppler Velocity Index (DVI)
- Grade of aortic transvalvular regurgitation
- Grade of aortic paravalvular regurgitation
- Grade of mitral regurgitation
- ERO for MR (if available)
- Max tricuspid regurgitant (TR) jet velocity (if TR is present)
- Left ventricular (LV) end-diastolic diameter (LVEDD)
- Left ventricular (LV) end-systolic diameter (LVESD)
- Interventricular septal thickness at end diastole
- Left ventricular posterior wall thickness at end diastole
- Left atrial diameter (AP linear dimension) at systole
- Left ventricular ejection fraction by visual estimate
- Heart rate
- Mitral inflow "A" velocity
- Mitral inflow "E" velocity
- Mitral inflow deceleration time
- Mitral annular tissue Doppler systolic (s) velocity (septal and lateral)
- Mitral annular tissue Doppler early diastolic (e') velocity (septal and lateral)
- Mitral annular tissue Doppler late diastolic (a') velocity (septal and lateral)

In addition, the following variables will be derived by the central database from the appropriate measurements reported by the Echo Core Lab:

- **Mean Transvalvular Gradient (Mean  $\Delta P$ ) Across the Prosthetic Valve in mmHg**  

$$\text{Mean } \Delta P = \text{MG}_{V_2} - \text{MG}_{V_1}$$
 Where:  $\text{MG}_{V_2}$  is the mean pressure gradient across the prosthesis in mmHg, and  $\text{MG}_{V_1}$  is the mean pressure gradient from the left ventricular outflow tract in mmHg

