- **Peak Pressure Gradient (Peak  $\Delta P$ ) Across the Aortic Prosthetic Valve in mmHg**  

$$\text{Peak } \Delta P = 4 \times (V_2^2 - V_1^2)$$
 Where:  $V_2$  is the peak velocity across the prosthesis in m/sec, and  $V_1$  is the peak velocity from the left ventricular outflow tract in m/sec
- **Effective Orifice Area (EOA) in  $\text{cm}^2$**   

$$\text{EOA} = \text{LVOT Long Axis diameter}^2 \times 0.785 \times (\text{VTI}_{V_1} / \text{VTI}_{V_2})$$
 Where:  $\text{VTI}_{V_1}$  is the velocity time integral of the left ventricular outflow tract in cm, and  $\text{VTI}_{V_2}$  is the velocity time integral of the aortic prosthesis in cm. Alternatively, using velocity instead of VTI for simplification:  

$$\text{AVA} = \pi(\text{radius of LVOT})^2 \times V_{\text{LVOT}} / V_{\text{max}}$$
 Where  $V_{\text{max}}$  is the maximum flow velocity across aortic valve,  $V_{\text{LVOT}}$  is the maximum velocity across the LVOT.
- **Effective Orifice Area Index (EOAI) in  $\text{cm}^2/\text{m}^2$**   

$$\text{EOAI} = \text{EOA} / \text{BSA}$$
 Where: EOA is the effective orifice area in  $\text{cm}^2$ , and BSA is the body surface area in  $\text{m}^2$
- **Doppler Velocity Index = Velocity Time Integral Ratio (VTI Ratio)**  

$$\text{DVI} = \text{VTI Ratio} = \text{VTI}_{V_1} / \text{VTI}_{V_2}$$
 Where:  $\text{VTI}_{V_1}$  is the velocity time integral of the left ventricular outflow tract in cm, and  $\text{VTI}_{V_2}$  is the time velocity integral of the prosthetic aortic valve in cm
- **Stroke Volume (SV) in ml/beat**  

$$\text{SV} = \text{LVOT long axis diameter}^2 \times 0.785 \times \text{VTI}_{V_1}$$
 Where:  $\text{VTI}_{V_1}$  is the velocity time integral from the left ventricular outflow tract in cm
- **Cardiac Output (CO) in l/min**  

$$\text{CO} = (\text{SV} \times \text{HR}) / 1000$$
 Where: SV is the stroke volume in ml/beat, and HR is the heart rate in beats per minute
- **Left Ventricular Mass (LVM) in grams**  

$$\text{LVM} = 0.83 \times [(\text{LVEDD} + \text{LVPW} + \text{IVS})^3 - (\text{LVEDD})^3] + 0.6$$
 Where: LVEDD is the left ventricular end-diastolic diameter in cm, LVPW is the left ventricular posterior wall thickness at end diastole in cm, and IVS is the interventricular wall thickness at end diastole in cm.
- **Left Ventricular Mass Index (LVMI) in  $\text{g}/\text{m}^2$  body surface area**  

$$\text{LVMI} = \text{LVM} / \text{BSA}$$

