 Where: LVM is left ventricular mass in g, and BSA is body surface area in  $\text{m}^2$
- **Fractional Shortening (FS) in %**  

$$\text{FS} = [(\text{LVEDD} - \text{LVESD}) / \text{LVEDD}] \times 100$$
 Where: LVEDD is left ventricular end-diastolic diameter in cm, and LVESD is left ventricular end-systolic diameter in cm
- **Estimated Right Ventricular Systolic Pressure (RVSP) in mmHg**  

$$\text{RVSP} = (4 \times \text{MV}_{\text{TR jet}}^2) + 10$$
 Where:  $\text{MV}_{\text{TR jet}}$  is the max velocity of the tricuspid regurgitant jet, and 10 = the assumed mean right atrial pressure in mmHg

- **Aortic Regurgitant volume (ml/beat) and fraction (%)**

The regurgitant volume across the aortic valve may be calculated as the difference between the LVOT volume and the transmitral volume, assuming there is no significant mitral regurgitation

$RV = \text{Total stroke volume} - \text{forward stroke volume}$

$RV = SV_{AV} - SV_{MV}$

$RF = [RV/SV] \times 100$

$SV_{AV} = 0.785 \times (LVOT)^2 \times VTI_{LVOT}$  (by Pulsed-wave Doppler)

$SV_{MV} = 0.785 \times (D_{MV})^2 \times VTI_{MV}$  (by Pulsed-wave Doppler)

Where: SV is stroke volume in mL, AV is aortic valve and MV is mitral valve

- **Regurgitant Orifice Area (EROA)**

The regurgitant orifice area or EROA represents the average size of the defect in the aortic valve during diastole and is proportional to regurgitant severity.

The regurgitant orifice area may be calculated as the regurgitant volume multiplied by the VTI of the continuous wave Doppler jet

$EROA_{AV} = RV / VTI_{ARjet}$  (by Continuous-wave Doppler)

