Diastolic flow reversal in the descending aorta—PW	Absent or brief early diastolic	Intermediate	Prominent, holodiastolic
Circumferential extent of prosthetic valve paravalvular regurgitation (%)‡‡	<10%	10-29%	≥30%
Quantitative Parameters‡			
Regurgitant volume (ml/beat)	<30 ml	30-59 ml	≥60 ml
Regurgitant fraction (%)	<30%	30-49%	≥50%
EROA (cm  )	<0.10 cm 	0.10-0.29 cm 	≥0.30 cm 

\*In conditions of normal or near normal stroke volume (50–70 mL)

†These parameters are more affected by flow, including concomitant aortic regurgitation

‡For LVOT >2.5 cm, significant stenosis criteria is <0.20

†Use in setting of BSA ≥1.6 cm^2 (note: dependent on the size of the valve and the size of the native annulus)

§Use in setting of BSA <1.6 cm^2

\*\*Use in setting of BMI <30 kg/cm^2

††Use in setting of BMI ≥30 kg/cm^2

‡‡Not well-validated and may overestimate severity compared to quantitative Doppler

Moderate or severe AS and AR will be considered a serious adverse event when the dysfunction is accompanied with clinical sequelae at the time of the event detection, and the clinical sequelae are chronologically and physiologically associated with the dysfunction.

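### The BSA formula in section C.4.1 takes height in metres with a coefficient that needs centimetres; followed literally it makes BSA 28 times too small

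*Combined protocol and SAP*

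**What the plan says.** Section C.4.1 (Screening Procedures) lists BSA with height and weight in the physical examination and says "BSA will be calculated from height and weight by use of the formula by Dubois and Dubois". The expression that follows is 0.007184 × weight^0.425 × height^0.725, with weight labelled kg and height labelled m.

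BSA is used in these places:

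- Inclusion criterion 3a (C.3.6.1) is met by a valve area of at most 1.0 cm² or by an "aortic valve area index" below 0.6 cm²/m².
- Appendix R.7, section 18 divides effective orifice area (EOA) by BSA to get the indexed area (EOAI), where "BSA is the body surface area in" m². LV mass index (LVMI) is formed the same way. The section says that "the following variables will be derived by the central database from the appropriate measurements reported by the Echo Core Lab".
- The Prosthetic Valve Dysfunction table in O.2 grades prosthesis-patient mismatch on indexed EOA. It also has two rows of EOA thresholds, chosen by notes that begin "Use in setting of BSA" and split at 1.6.
- Device success (C.6.8.2, item 20) requires no mismatch, and procedural success (item 21) requires device success.

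**The concern.** This is an operative formula, not background text. A site or programmer who follows it literally gets a BSA of less than a tenth of a square metre for every adult, and every quantity indexed to BSA moves by the same factor. At stake are one of the two routes through criterion 3a, the mismatch component of device and procedural success, the choice of EOA threshold for valve dysfunction, and LVMI.

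The threshold choice also bears on comparisons between arms. Clinical Efficacy and Time-Related Safety (C.6.8.1, items 5 and 6) define valve-related dysfunction with an EOA limit written as a range, 0.9 to 1.1 cm². The only rule the protocol offers for choosing within that range is the BSA split in O.2.

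**Working it through.** The documents state no computed BSA, so there is no figure to reproduce. They also give no heights or weights; the body sizes below are assumptions meant to span adult patients.

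**Formula.** BSA = 0.007184 × W^0.425 × H^0.725, with W in kg. Changing H from metres to centimetres multiplies the result by 100^0.725 = 28.18, whatever the weight.

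| Weight, height | BSA, H in m (as printed) | BSA, H in cm |
|---|---|---|
| 45 kg, 145 cm | 0.0474 | 1.337 |
| 60 kg, 160 cm | 0.0576 | 1.622 |
| 75 kg, 170 cm | 0.0661 | 1.864 |
| 95 kg, 180 cm | 0.0762 | 2.148 |
| 150 kg, 200 cm | 0.0999 | 2.815 |

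**Check against the protocol's own scale.**

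- The O.2 notes split subjects at BSA 1.6. With the printed formula and a height of 2.00 m, reaching 1.6 needs a weight of (1.6 / (0.007184 × 2.00^0.725))^(1/0.425), which is above 100,000 kg.
- Criterion 3a gives a second check. Its two limits coincide at 1.0 / 0.6 = 1.67 m², again the size that the centimetre version produces.

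**Effects if the formula is applied as printed.**

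1. *Criterion 3a.* An index below 0.6 means a valve area below 0.6 × BSA. At 75 kg and 170 cm that is 0.6 × 0.0661 = 0.040 cm² as printed, against 0.6 × 1.864 = 1.12 cm². The index route is therefore closed. Patients with an area of at most 1.0 cm² still qualify, so at this body size only areas above 1.0 and below 1.12 cm² are affected. A patient with true BSA below 1.67 m² is not affected at all, because 0.6 × BSA is then below 1.0. Example at 95 kg and 180 cm with an area of 1.05 cm²: 1.05 / 2.148 = 0.49 (qualifies), but 1.05 / 0.0762 = 13.8 as printed (does not).
2. *Mismatch.* Indexed EOA above 0.85 is insignificant when BMI is below 30, and above 0.70 when BMI is 30 or more. At 75 kg and 170 cm, the printed formula puts the 0.85 limit at an EOA of 0.85 × 0.0661 = 0.056 cm². Even an EOA of 0.8 cm² at 150 kg and 200 cm indexes to 8.0. Every subject would grade insignificant. Example at 95 kg and 180 cm with an EOA of 1.3 cm²: BMI is 95 / 1.80² = 29.3, so the 0.85 and 0.65 limits apply; 1.3 / 2.148 = 0.61 is severe, but the printed formula gives 1.3 / 0.0762 = 17.1, insignificant.
3. *EOA thresholds.* All printed values are at most 0.10, so every subject falls in the row for BSA below 1.6. A subject with true BSA of 1.6 or more and an EOA of 1.0 cm² would be graded normal on that parameter (limit 0.9) instead of mild (limit 1.1). At 0.7 cm² the grade would be mild (limit 0.6) instead of moderate/severe (limit 0.8).
4. *LVMI* would be 28.18 times too large.

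**What does not use BSA.** The primary endpoint is death or disabling stroke (C.6.5). The sample size (C.6.5.2) rests on event rates and a margin. The labelling hierarchy (C.6.10.1) tests EOA in cm² and mean gradient in mmHg, both unindexed, and none of its other items is indexed to BSA.

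**The case against.** The strongest case against is that this is a misprint with no demonstrated effect. The protocol names the formula, so a programmer may well have used the standard version. Indexed echo variables are derived centrally rather than by hand at sites, and a BSA near 0.07 m² for every adult would be conspicuous in any data review. The text available shows no code and no computed BSA.

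Much of this stands. A reader might infer that every BSA in the trial is 28 times too small, that device success is inflated, and that all BSA-indexed endpoints are wrong. The documents do not support that: each of those statements needs the printed unit to have been implemented, which is unknown.

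The reach is also limited. Criterion 3a keeps its independent area route. Device success is assessed in the TAVI arm only and is descriptive, with no hypothesis test. EOAI and LVMI are derived variables, not listed secondary endpoints.

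What does not stand is that the printed rule can be left alone. It contradicts the protocol's own 1.6 cut-off. If it was followed, an eligibility route and several derived quantities are wrong; if it was not, the protocol does not describe what was done.

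**Conclusion.** The formula is wrong as written: the height unit does not match the coefficient, and literal use understates BSA by a factor of 28.18 for any body size. That much needs no assumption beyond the protocol's own BSA scale.

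The downstream effects are conditional on literal use. They are confined to the index route of criterion 3a for patients with a valve area above 1.0 cm², mismatch within device and procedural success, the BSA-dependent EOA thresholds for valve dysfunction, EOAI and LVMI. The size of the eligibility band and the grading examples rest on the assumed heights and weights; the factor itself does not. Confirmatory inference is unaffected.

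**What to change.** In C.4.1, change the unit of height from m to cm. Alternatively keep metres and change the coefficient to 0.007184 × 28.18 = 0.2025. Confirm and document which version the EDC system and the central database compute. Re-derive BSA, valve area index, EOAI, mismatch and LVMI, with the EOA grading that depends on BSA, only if the printed version was programmed. No threshold or eligibility limit changes. The cost is a one-word correction and one programming check.

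Two separate copy-edits can go in the same amendment; neither adds weight to this point:

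- The O.2 table notes label BSA in cm² and BMI in kg/cm²; these should read m² and kg/m².
- Appendix R.7, section 18 says "The regurgitant orifice area may be calculated as the regurgitant volume multiplied by the VTI of the continuous wave Doppler jet", while the expression beneath it divides. Division is the one consistent with EROA graded in cm² in O.2 (mL divided by cm), so the sentence should say divided.
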